7.2 Pre-Study Assessments (All Patients)

Prior to performing any procedures or assessments, the nature of the study and the potential risks associated with the trial will be explained to all patient candidates and written informed consent will be obtained. Patients who choose to participate will have to consent to the biobanking program and will be asked to sign the mandatory section in the main study consent form related to biobank samples. Evaluations obtained as part of routine medical care and performed during the screening period may be used in place of the study specific evaluations. Patients will acknowledge and agree to the possible use of this information for the study by giving informed consent.

7.2.1 Screening (All patients)

All pre-treatment evaluations are to be performed within 28 days of Day 1 unless otherwise noted.

- Informed Consent
- TP53 mutation confirmation – send local report to vendor (see lab manual for instructions)
- Medical history – must include a thorough assessment and documentation of all transfusions received beginning from 8 weeks prior to randomization to end of treatment/off treatment; record transfusions on transfusion log.
- Physical examination
- Height
- Weight
- ECOG performance status
- Creatinine clearance (Cockcroft-Gault method; see [Appendix IV](#))
- Vital signs: including blood pressure, heart rate, respiration rate and temperature
- Hematology: hemoglobin, hematocrit, MCV, platelet count, blasts, WBC and WBC differentials.
- Blood chemistry including sodium, potassium, BUN, glucose, ALT/AST, alkaline phosphatase, total protein, total bilirubin, albumin, creatinine, calcium, chloride and magnesium.
- Serum pregnancy test: For patients with reproductive potential.
- ECG: Standard 12-lead ECGs to be performed with patient in a semi-recumbent position in triplicate.
- Concomitant medication
- Bone marrow aspirate and biopsy - Bone marrow assessment completed within 28 days of signing consent will be accepted to fulfill screening requirement as long as it has been completed following the last MDS treatment (excluding ESAs).
- Baseline bone marrow aspirate and biopsy core for exploratory objectives. If no aspirate is available, then peripheral blood is acceptable.
- Adverse Events: baseline, at the time of eligibility confirmation.

7.2.2 Randomization

Randomization will occur after screening, once a patient has had their eligibility confirmed, has agreed to participate and is ready to start on the study treatment.

Stratified randomization will be based on age group (< 65 years and ≥ 65 years). Patients will be assigned to one of two strata based on age group (< 65 years and ≥ 65 years), and then assigned to the particular treatment arm from the randomization list for that stratum. Randomization will be balanced within each stratum with patients randomly assigned with equal probability (1:1 allocation) to one of the two treatment arms (APR-246 + azacitidine or azacitidine). Permuted block randomization (random allocation within block) will be used to assign patients to treatments within each stratum.

7.3 Experimental Arm (APR-246 + Azacitidine)

In the event that a visit or test cannot be scheduled on the exact visit day, a window of ±3 days is allowable.

7.3.1 Cycle 1

7.3.1.1 Days 1-10

Day 1 examinations marked * do not need to be repeated if already performed within 3 days prior to day 1 cycle 1.

- Transfusion log: must capture all transfusions beginning from 8 weeks prior to randomization to end of treatment/off treatment.
- Adverse Events: All adverse events since the last visit should be recorded. Even though pre-medicated, patients should be closely monitored.
- Concomitant medications.
- Physical examination: Day 1* weight, body surface area.
- ECOG performance status: Day 1.
- Vital signs. **Before infusion**, 2 hours into **each** infusion (± 30 min) and at EOI (± 30 min)
- Hematology: Day 1* hemoglobin, hematocrit, MCV, platelet count, blasts, WBC and WBC differentials.
- Blood chemistry: Day 1* sodium, potassium, BUN, glucose, ALT/AST, alkaline phosphatase, total protein, total bilirubin, albumin, creatinine, calcium, chloride and magnesium.
- ECG: Standard 12-lead ECG to be performed with patient in a semi-recumbent position; pre-dose (prior to the PK blood draw before the infusion) and at the end of infusion, per Table 10.
- Pharmacokinetics for APR-246: on Days 1, 2, 4, per Section 8.3

- APR-246 administration.
- Azacitidine administration. Administered daily for 7 consecutive days starting on Day 4 (Days 4 to 10 inclusive). The same route should be maintained over the 7-day treatment period (whichever route is used on Day 4, the other days should follow the same method route of administration). On Day 4 azacitidine is given immediately after APR-246 infusion.
- Pharmacokinetics for azacitidine: Day 4, per Section 8.3 (at selected sites only)

7.3.1.2 Week 2 (Day 8 ± 3 Day)

- Adverse events
- Concomitant medications
- Hematology
- Blood chemistry

7.3.1.3 Perform Weekly

- Adverse events
- Concomitant medications
- Hematology weekly
- Blood chemistry weekly

7.3.2 Cycle 2 Day 1 ± 3 Day (same as Cycle 1 Day 29)

Tests should be performed prior to first dose

Day 1 examinations marked * do not need to be repeated if already performed within 3 days prior to day 1 of cycle 2.

- Adverse Events: All adverse events since the last visit should be recorded. Even though pre-medicated, patients should be closely monitored.
- Concomitant medications.
- Physical examination: Day 1* weight, body surface area.
- ECOG performance status: Day 1.
- Vital signs.
- Hematology: Day 1* hemoglobin, hematocrit, MCV, platelet count, blasts, WBC and WBC differentials.
- Blood chemistry: Day 1* sodium, potassium, BUN, glucose, ALT/AST, alkaline phosphatase, total protein, total bilirubin, albumin, creatinine, calcium, chloride and magnesium.
- ECGs pre-dose. Standard 12-lead ECGs to be performed in triplicate on Day 1 with patient in a semi-recumbent position. Perform prior to the PK blood draw before infusion, per Table 10.

7.3.2.1 Days 1-10

- Adverse events: All adverse events since the last visit should be recorded. Even though pre-medicated, patients should be closely monitored.
- Concomitant medications.
- Vital signs. Before infusion, then 2 hours into each infusion (± 30 min) and at EOI (± 30 min)
- APR-246 administration (Days 1 – 4).
- Azacitidine administration. Administered daily for 7 consecutive days starting on Day 4 (Days 4 to 10 inclusive). The same route should be maintained over the 7-day treatment period (whichever route is used on Day 4, the other days should follow the same method route of administration). On **Day 4** azacitidine is given immediately after APR-246 infusion.
- Pharmacokinetics for APR-246: Cycle 2 and 3: Days 1, 2, 4

7.3.2.2 Week 2 (Day 8 \pm 3 Day)

- Adverse events
- Concomitant medications
- Hematology
- Blood chemistry

7.3.2.3 Week 3 (Day 15 \pm 3 Day)

- Adverse events
- Concomitant medications
- Hematology
- Blood chemistry

7.3.2.4 Week 4 (Day 22 \pm 3 Day) (Rest Period)

- Adverse events
- Concomitant medications
- Hematology
- Blood chemistry

7.3.2.5 End of Cycle 2

- Bone marrow/response assessment
- Bone marrow aspirate and biopsy core for exploratory objectives. If no aspirate is available, then peripheral blood is acceptable.

7.3.3 Cycle 3 Day 1 \pm 3 Day (same as Cycle 2 Day 29) and Onwards (Cycle 4+)

These tests should be performed prior to first dose

- Adverse Events: All adverse events since the last visit should be recorded. Even though pre-medicated, patients should be closely monitored.
- Concomitant medications.
- Physical examination: Day 1* weight, body surface area.
- ECOG performance status: Day 1.
- Vital signs.
- Hematology: Day 1* hemoglobin, hematocrit, MCV, platelet count, blasts, WBC and WBC differentials.
- Blood chemistry: Day 1* sodium, potassium, BUN, glucose, ALT/AST, alkaline phosphatase, total protein, total bilirubin, albumin, creatinine, calcium, chloride and magnesium.
- ECGs: see Table 10.

7.3.3.1 Days 1-10

- Adverse Events: All adverse events since the last visit should be recorded. Even though pre-medicated, patients should be closely monitored.
- Concomitant medications.
- Vital signs. Before infusion, then 2 hours into each infusion (\pm 30 min) and at EOI (\pm 30 min)
- APR-246 administration (Days 1 – 4).
- Azacitidine administration. Administered daily for 7 consecutive days starting on Day 4 (Days 4 to 10 inclusive). The same route should be maintained over the 7-day treatment period (whichever route is used on Day 1, the other days should follow the same method route of administration). On **Day 4** azacitidine is given immediately after APR-246 infusion
- ECG: Standard 12-lead ECGs to be performed with patient in semi-recumbent position:
 - Day 1 only: Perform prior to the PK blood draw before infusion, per Table 10.
- Cycle 3 Only: Pharmacokinetics APR-246 as per Section 8.3
- Hematology weekly
- Blood chemistries weekly

7.3.3.2 Week 2 (Day 8 \pm 3 Day)

- Adverse events
- Concomitant medications
- Hematology. For patients with documented CR at disease assessment following cycle 2, hematology and blood chemistry assessments will be required for D1 of each subsequent cycle and more frequently per the discretion of the treating

physician.

- Blood chemistry. For patients with documented CR at disease assessment following cycle 2, hematology and blood chemistry assessments will be required for D1 of each subsequent cycle and more frequently per the discretion of the treating physician.

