- i. **Bone marrow aspirate sample and biopsy core is collected at baseline and when bone marrow is sampled for disease assessment. If no aspirate is available, then peripheral blood is acceptable. Bone marrow assessment completed within 28 days of signing consent will be accepted to fulfill screening requirement, as long as it has been completed following the last MDS treatment (excluding ESAs (erythropoietic stimulating agent)).**
- j. Hematology including hemoglobin, hematocrit, MCV, platelet count, blasts, WBC and WBC differentials weekly. **The peripheral blood sample collected on Day 1 of each cycle starting at Cycle 2 will be for disease assessment, if bone marrow aspirate is not available (see footnote r).** For patients with documented CR at disease assessment following Cycle 2, hematology and blood chemistry assessments will be required for D1 of each subsequent cycle and more frequently per the discretion of the treating physician. Otherwise performed weekly until CR.

- k. Blood chemistry including sodium, potassium, BUN, glucose, ALT/AST, alkaline phosphatase, total protein, total bilirubin, albumin, creatinine, calcium, chloride and magnesium weekly. At screening, the creatinine clearance may be calculated from the serum creatinine. A 24-hour urine for Creatinine Clearance may be performed at investigator's discretion. For patients with documented CR at disease assessment following Cycle 2, hematology and blood chemistry assessments will be required for D1 of each subsequent cycle and more frequently per the discretion of the treating physician. Otherwise perform weekly until CR.
- l. Pregnancy test; for women of childbearing potential, a negative pregnancy test (urine or serum) must be documented between Screening and first day of treatment on study. Must be documented prior to 1st dose of treatment on study.
- m. Standard 12-lead ECGs to be performed in triplicate at baseline/screening, on Days 1 - 4 of Cycle 1 (experimental arm only) and on Days 1 of each subsequent cycle (experimental arm only) with patient in a semi-recumbent position. Please consult Table 10 for ECG collection schedule.
- n. Please consult section 8.3, Table 9 for PK collection schedule.

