7.4.2 Perform Weekly

- Adverse events
- Concomitant medications
- Hematology
- Blood chemistry

7.4.3 End of Odd Numbered Cycles Up to Month 12

- Response assessment, based on peripheral blood

7.4.4 End of Even Numbered Cycles Up to and Including Month 12

- Bone marrow sample for response assessment
- Bone marrow aspirate and biopsy core for exploratory objectives. If no aspirate is available, then peripheral blood is acceptable.

7.4.5 After Month 12

Every 3 Month Visits:

- Adverse events
- Concomitant medications
- Bone marrow aspirate and biopsy / Response assessment
- Bone marrow aspirate and biopsy core for exploratory objectives. If no aspirate is available, then peripheral blood is acceptable.
- CBCs as needed.

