8.1.1 Safety Analysis

Safety data including AEs, vital signs, laboratory data, ECG, and physical exam will be tabulated for the safety population. Adverse events will be tabulated by body system, preferred term, severity, and relationship to treatments. The tabulation of laboratory parameters will include the normal ranges for each parameter. Each value will be classified as falling above, below, or within the normal range. Laboratory parameters will also be tabulated by maximum NCI-CTCAE severity grade.

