APPENDIX I – ECOG PERFORMANCE STATUS

Grade

- | | |
|---|--|
| 0 | Fully active, able to carry on all pre-disease performance without restriction. |
| 1 | Restricted in physically strenuous activity but ambulatory and able to carry out work of a light or sedentary nature, e.g., light house work, office work. |
| 2 | Ambulatory and capable of all self-care but unable to carry out any work activities. Up and about more than 50% of waking hours. |
| 3 | Capable of only limited self-care, confined to bed or chair more than 50% of waking hours. |
| 4 | Completely disabled. Cannot carry on any self-care. Totally confined to bed or chair. |
| 5 | Dead. |

**APPENDIX II – PROPOSED MODIFIED INTERNATIONAL WORKING GROUP
 RESPONSE CRITERIA FOR ALTERING NATURAL HISTORY OF MDS**

(from Cheson et al, Blood 2006)

Category	Definition
Complete remission (CR)	Bone marrow blasts $\leq 5\%$ myeloblasts with normal maturation of all cell lines* Persistent dysplasia will be noted* [‡] Peripheral blood \diamond Hemoglobin (Hgb) ≥ 11 g/dL Platelets $\geq 100 \times 10^9/L$ Neutrophils $\geq 1.0 \times 10^9/L$ \ddagger Blasts 0%
Partial remission (PR)	All CR criteria if abnormal before treatment except: Bone marrow blasts decreased by $\geq 50\%$ over pretreatment but still $> 5\%$ Cellularity and morphology not relevant
Marrow CR \neq	Bone marrow: $\leq 5\%$, myeloblasts and decrease by $\geq 50\%$ over pretreatment \ddagger Peripheral blood: if HI responses, they will be noted in addition to marrow CR \ddagger
Stable disease	Failure to achieve at least PR $<$ but no evidence of progression for > 8 weeks
Failure	Death during treatment or disease progression characterized by worsening of cytopenias, increase in percentage of bone marrow blasts, or progression to a more advanced MDS FAB subtype than pretreatment
Relapse after CR or PR	At least 1 of the following: Return to pretreatment bone marrow blast percentage Decrement of $\geq 50\%$ from maximum remission/response levels in granulocytes or platelets Reduction in Hgb concentration by ≥ 15

	g/dL or transfusion dependence
Cytogenic response	Complete = Disappearance of the chromosomal abnormality without appearance of new ones Partial = at least 50% reduction of the chromosomal abnormality

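### The post-CR laboratory schedule contradicts itself; read by arm, it requires about four counts per cycle in control patients in CR and one in experimental patients, which could shift relapse dates slightly

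*Combined protocol and SAP*

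**What the plan says.** Four places in the protocol set the frequency of hematology and chemistry after CR.

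- **Section 7.3.3.2 (experimental arm, Cycle 3 onward):** "For patients with documented CR at disease assessment following cycle 2, hematology and blood chemistry assessments will be required for D1 of each subsequent cycle". The sentence goes on to allow more frequent testing at the treating physician's discretion. Sections 7.3.3.3 and 7.3.3.4 make the Week 3 and Week 4 tests as-needed by reference back to it.
- **Section 7.3.3.1 (same arm, same cycles):** "Hematology weekly", and chemistry likewise, with no exception for CR.
- **Control arm:** the section headed "7.4.2 Perform Weekly" lists hematology and chemistry, with no exception for CR.
- **Footnotes j and k to the Schedule of Study Evaluations:** "For patients with documented CR at disease assessment following Cycle 2, hematology and blood chemistry assessments will be required for D1 of each subsequent cycle", followed by "Otherwise performed weekly until CR" for hematology and "Otherwise perform weekly until CR" for chemistry. No arm is named.

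Two analyses use these data. Appendix II lets relapse after CR be met by a fall of at least 50% "from maximum remission/response levels in granulocytes or platelets", and Section 9.3.1 ends duration of response at relapse, progression or death. For safety, Section 8.1.1 states: "Laboratory parameters will also be tabulated by maximum NCI-CTCAE severity grade"; Section 9.3.3 plans the same summary.

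**The concern.** Duration of CR stands beside the CR rate in the primary objective (Section 3.1). If one arm has its counts taken weekly after CR and the other once per cycle, the same fall in platelets or granulocytes is seen sooner in the first arm. Its duration of CR then looks shorter for a reason unrelated to the drug. The relapse date also feeds relapse-free survival. Sections 8.2.1 and 9.3.1 do not restrict the relapse date to the formal response visits, so a weekly count could set it.

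The highest grade seen in a patient can only stay the same or rise as samples are added. If the number of samples differs by arm, the maximum-grade laboratory tables do not compare like with like. This matters because Section 2.8.1 says that a contribution of APR-246 to chemotherapy-induced marrow suppression has been neither shown nor excluded.

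**Working it through.** **1. The plan's own figure.** The sample counts below use the planned CR rates, so I checked the power statement in Section 9.1 first: 77 per arm, 50% v 25%, two-sided alpha 0.05. With the pooled normal approximation:

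Power = Φ[(0.25 − 1.96·√(2·0.375·0.625/77)) / √((0.25 + 0.1875)/77)] = Φ[(0.25 − 0.1529)/0.0754] = Φ(1.288) = 90.1%.

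The stated 90% reproduces. The present point does not depend on it.

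**2. Required counts per 28 days for a patient in CR**

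| Reading | Experimental | Control |
|---|---|---|
| Arm sections (7.3.3.2 to 7.3.3.4 v 7.4.2) | 1 | 28/7 = 4 |
| Footnotes j and k | 1 | 1 |
| Section 7.3.3.1 with 7.4.2 | 4 | 4 |

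One is a minimum, because of the discretion clause. The exception is worded for CR documented after Cycle 2. Its use for later CRs rests only on the until-CR wording in the footnotes.

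**3. Dating of a count-based relapse under the arm sections.** The mean wait to the next count is half the interval: 28/2 − 7/2 = 14 − 3.5 = 10.5 days. For a single relapse the gap is 0, 7, 14 or 21 days, about equally likely, which also averages 10.5. Table 1 (footnotes) gives median response durations of 5.7 and 7 months in patients with mutated *TP53*, about 174 and 213 days: 10.5/174 = 6.0% and 10.5/213 = 4.9%.

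As a check, exponential CR durations were simulated (2,000,000 per setting), with the same true duration in both arms, and read on the two grids. The 12-month row is an assumption, included to show the range.

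| True median | Mean delay, 28-day | Mean delay, 7-day | Gap (days) | Apparent HR (7-day mean / 28-day mean) | Median as read, 28-day v 7-day (days) |
|---|---|---|---|---|---|
| 5.7 months | 14.3 | 3.5 | 10.7 | 0.96 | 196 v 175 |
| 7 months | 14.2 | 3.5 | 10.7 | 0.97 | 224 v 217 |
| 12 months | 14.1 | 3.5 | 10.6 | 0.98 | 392 v 371 |

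The planned Kaplan-Meier median moves in steps of the grid, so its gap varies with where the true median falls: 21, 7 and 21 days here. All these figures assume that every relapse is count-based, that no discretionary counts are drawn, and that weekly control counts continue throughout.

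**4. Required laboratory samples per patient over six cycles.** Assumptions: the planned CR rates, every CR documented by the end of Cycle 2, and all patients on treatment for six cycles.

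- Cycles 1 and 2, both arms: 2 × 4 = 8.
- Cycles 3 to 6, experimental: 4 × (0.5×1 + 0.5×4) = 4 × 2.5 = 10; total 18.
- Cycles 3 to 6, control under the footnotes: 4 × (0.25×1 + 0.75×4) = 4 × 3.25 = 13; total 21.
- Cycles 3 to 6, control under Section 7.4.2: 4 × 4 = 16; total 24.

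The experimental arm has 1 − 18/21 = 14% fewer required samples under the footnotes and 1 − 18/24 = 25% fewer under Section 7.4.2. The deficit shrinks if CRs come later.

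**The case against.** A reader might infer that the plan itself looks for relapse and toxicity more often in the control arm. The documents do not support that. Footnotes j and k apply the reduction to patients in general, whereas footnotes f, g and m name an arm where a rule is arm-specific. On the footnotes' reading, CR patients in both arms have the same required schedule. Day 1 is a floor, and Section 7.3.3.1 even keeps the experimental arm weekly. The Schedule grid (Table 8) is not in the text available for this review, so its cells could not be checked.

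The effect on duration of CR is also limited. Footnote r sets response assessment every 4 weeks in both arms, and after Month 12 both arms have blood counts as needed. Appendix II does not end a response for transient cytopenia between courses if counts recover, so many mid-cycle falls could not establish relapse at once. Relapse by marrow blasts does not depend on weekly counts. Section 9.3.1 specifies only a median and interval per arm for duration of CR, without a between-arm test.

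A reader might also infer 23% to 38% fewer samples behind the maximum grade (1 − 2.5/3.25 and 1 − 2.5/4). Those ratios describe only cycles after CR and leave out the weekly samples of Cycles 1 and 2. Nor does it follow that the experimental arm will show fewer high-grade values: if CR patients stay on treatment longer, that arm may accrue more samples in total.

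All of this stands and limits the size of the problem. It does not settle which text a control-arm site should follow. Discretion does not remove the ambiguity either, because in an open-label trial discretionary testing can itself differ by arm.

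**Conclusion.** The contradiction is real and touches an outcome in the primary objective, but its likely effect is small. Only if sites follow the arm-specific sections does the required post-CR frequency differ, about four counts to one per 28 days. The resulting shift in count-based relapse dates then averages at most about 10.5 days, with an apparent hazard ratio of about 0.96 to 0.98 in favor of the experimental arm under no true effect. That is an upper bound on the average, under the assumptions in step 3. The CR-rate test is not affected, since the reduction begins only after CR is documented.

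Under the footnotes there is no scheduled difference between CR patients. Sampling still depends on response, so the arm with more CRs has somewhat fewer required samples: 14% over six cycles, or 25% if Section 7.4.2 governs the control arm. The net direction for the maximum-grade tables is uncertain because time on treatment also matters.

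**What to change.** 1. Reconcile Sections 7.3.3.1 to 7.3.3.4, Section 7.4.2 and footnotes j and k so that one identical post-CR laboratory schedule applies to both arms. State whether it covers a CR first documented after Cycle 2. Which frequency to adopt is for the sponsor to decide.
2. For the duration-of-CR analysis, date count-defined relapse at scheduled time points common to both arms: Day 1 of each cycle and the response-assessment visits. Repeat the analysis with all counts used for dating, as a sensitivity analysis.
3. Keep the all-samples maximum-grade table as the main safety table. A table restricted to scheduled samples common to both arms may be added as supportive. It should not replace the main table, because it would drop weekly on-treatment values, including those of patients not in CR (50% and 75% of the arms at the planned rates).

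The cost is a few sentences, one derivation rule and one sensitivity analysis; no new procedure is needed for the dating rule. The downside is that some relapse dates are recorded slightly later in the main analysis.
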